All US-guided hip injections will be completed using a cart-based Philips ultrasound machine in either the Sports Medicine Center, Mayo-14 PM&R Clinic, or Gonda Musculoskeletal Clinic. US-guided local anesthetic administration will be completed using a 25-gauge, 2-inch stainless steel needle. US-guided hip injections will be completed using a 22-gauge, 3.5-inch stainless steel needle. The equipment for this study is available in each respective clinic and will be used at no additional cost.

Study Subjects

Mayo Clinic patients 18-75 years old referred for US-guided intraarticular hip injections in the Sports Medicine Center, Mayo-14 PM&R Clinic, or Gonda-14 Musculoskeletal Clinic.

Exclusion criteria will include: (1) chronic opioid use, (2) opioid use on day of procedure, (3) history of fibromyalgia or other diffuse chronic pain syndrome, (4) pain behavior during the clinical encounter as judged by the injectionist, or (5) anesthetic administration time outside the designated 5-15 second time frame.

Sample Size

The primary outcome will be the VAS for Pain score during local anesthesia infiltration. We will use two-sample t-tests to compare the mean VAS for Pain scores between the two groups at each of the three time points. Based on prior studies assessing the VAS for Pain, 14 can be considered the minimal clinically important difference when assessing moderate pain levels (10-12). At test significance level (α) = 0.05 with 80% power, a difference in means ($\mu_1 - \mu_2$) = 14 with common standard deviation (σ) = 20, i.e. an effect size ($\delta = |\mu_1 - \mu_2|/\sigma$) = 0.70, can be detected when the sample size (n) per group is 34 (68 total subjects). Since data will be collected at a single point of care, we anticipate a low dropout rate of approximately 10%. Therefore, total sample size for the study will be 76 patients after adjusting for dropouts.

Data Collection

Data collection is described above in *Study Design*. The non-injecting author ([name]) will collect and collate the data.

Data Handling/Processing

The data will be compiled on an Excel® file for data analysis. The computer files will be stored in the primary investigator's H-drive of Mayo Clinic's computer network.

Data Analysis

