Patient demographic characteristics data will be summarized and compared between the two treatment arms. Mean \pm SD for continuous variables and frequency (% percentage) for categorical variables will be given. Differences between arms will be tested using Wilcoxon tests for continuous variables and chi-square tests for categorical variables. Differences in adverse events between arms will be tested using chi-square tests. The mean VAS for Pain score prior to and during local anesthesia infiltration will be compared between the 2 groups by two-sample t-tests or Wilcoxon Rank sum tests when appropriate. Changes in pain from baseline will also be compared between arms using t-tests or Wilcoxon tests as appropriate. A generalized linear model (GLM) will be used to compare the two groups after adjusting for age, gender and baseline VAS pain score. Mixed effects models will be fit to model the longitudinal VAS pain scores. The primary analysis will be based on patients with anesthetic administered within the targeted 5-15 second infiltration window. However, an intent-to-treat analysis will also be performed, including patients that had anesthetic administered outside of the 5-15 second window. For all analyses, two-sided tests will be used and p-values less than 0.05 will be considered as statistically significant. All statistical analyses will be performed by SAS 9.3 version software (SAS institute Inc., Cary NC).

Adverse Event Stopping Rule

The stopping rule specified below is based on the knowledge available at study development. We note that the Adverse Event Stopping Rule may be adjusted in the event of either (1) the study re-opening to accrual or (2) at any time during the conduct of the trial and in consideration of newly acquired information regarding the adverse event profile of the treatments under investigation. The study team may choose to suspend accrual because of unexpected adverse event profiles that have not crossed the specified rule below. CTCAE v4.0, a grading system for adverse event severity, will be used to determine grading for these stopping rules.

Study accrual will be temporarily suspended if at any time we observe events considered at least possibly related to study treatment (i.e., an adverse event with attribute specified as “possible”, “probable”, or “definite”) that satisfy the following:

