- if 5 or more patients in the first 20 treated patients (or 25% of all patients after 20 are accrued) experience a grade 2 (moderate) or higher adverse event, and the adverse event incidence rate is higher in the BS arm than the lidocaine arm.

We note that we will review grade 4 (life-threatening) and 5 (death) adverse events deemed “unrelated” or “unlikely to be related”, to verify their attribution and to monitor the emergence of a previously unrecognized treatment-related adverse event.

After the first 20 patients are treated, accrual will also be temporarily suspended if there is significantly more pain after baseline on the BS arm.

Feasibility and Time Frame

Over 5,000 US guided injections are performed yearly in these three clinics combined, and a significant portion are intraarticular hip injections. We estimate it will take 6-12 months to recruit the patients. Patients will not need to be referred specifically for the study, as they will be recruited at the time of presentation for routine US guided hip injection. The study will likely add about 5-10 minutes to the typical US guided hip injection visit.

Strengths

There are several reasons this study has the potential to change the widespread practice of lidocaine local anesthesia prior to US guided hip joint injections. BS is a safe alternative local anesthetic with several potential advantages over lidocaine, including lower cost, less painful infiltration, and similar efficacy. Patients would be subjected to no additional risk or cost over routine US guided injections. Lower cost of BS would decrease health care costs. Less painful anesthetic infiltration and similar efficacy would minimize patient discomfort and improve patient experience.

Limitations

A limitation of this study design is that it will be specific to the hip joint, which is likely the US guided injection for which local anesthesia is most commonly used. Although similar efficacy would be expected in other body regions, the comparison of BS versus lidocaine may not be valid for other musculoskeletal injections.

Human Subjects:

Detailed Description and Population

For subject details and inclusion/exclusion criteria, see *Study Subjects* section above.

Research Materials

As noted above, pain will be assessed using a VAS for Pain scale.

Recruitment of Subjects

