All recruitment will occur directly with patients via a telephone call prior to their scheduled hip injection or at the point of care. An email will be sent to our PM&R and Sports Medicine colleagues to increase awareness and encourage internal referral for US guided intraarticular hip injections.

Potential Risks

The control group will receive the same treatment as is currently being provided with US guided hip joint injections. The BS group will be subjected to no increased risks relative to routine US guided hip joint injection. BS manufacturer indications include

subcutaneous and intramuscular injection. Animal studies have shown that 0.75% BS intramuscular and perineural injections cause no histological tissue damage (14,15). Furthermore, the BS manufacturer literature states “adverse reactions to intravenous, intramuscular, or subcutaneous injection of 0.9% benzyl alcohol are not known to occur in man... preparations containing 0.9% benzyl alcohol in several species of animals have indicated that an estimated intravenous dose of up to 30 mL may be safely given to an adult without toxic effects.” In this study, only 3 mL will be administered (subcutaneous/intramuscular) in each BS group subject.

Protection

Subjects will be provided with a contact number to call if any concerns arise. In the event of an adverse reaction or complication, the patient will be handled no differently than he/she would be following routine injections. Full evaluation and management will be provided as indicated.

As noted above in *Study Design*, subjects will be contacted 2 weeks post-procedure to assess for adverse events. After the first 20 patients have been completed, the non-injecting author ([name]) will assess the data for concerning trends in pain scores and adverse events in the BS group. If there are significantly elevated pain scores or more adverse events in the BS group, the study will be stopped.

Benefits

As noted above, preliminary studies have shown BS to be a safe alternative local anesthetic with potential advantages over lidocaine, including less painful infiltration and similar efficacy. BS has potential to minimize patient discomfort and improve patient experience associated with US guided injections without increasing procedural risks or cost.

Gender/Minority Mix:

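### The Protection section stops the study at 20 patients for more adverse events on BS, with no threshold, and conflicts with the guarded Adverse Event Stopping Rule covering the same patients

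*Combined protocol and SAP*

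**What the plan says.** Two sections govern the same early look.

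- **Human Subjects, Protection.** The look is set by "After the first 20 patients have been completed", and the action is: "If there are significantly elevated pain scores or more adverse events in the BS group, the study will be stopped". Nothing says which adverse events count, how large an excess is needed, or whether it is tested.
- **Adverse Event Stopping Rule.** The consequence and attribution are given by "Study accrual will be temporarily suspended if at any time we observe events considered at least possibly related to study treatment". The count is "if 5 or more patients in the first 20 treated patients (or 25% of all patients after 20 are accrued", and those patients must "experience a grade 2 (moderate) or higher adverse event, and the adverse event incidence rate is higher in the BS arm" than on lidocaine. This section also suspends accrual temporarily, rather than stopping the study, for significantly more pain on BS after 20 patients.

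The Data Analysis section bears on how the Protection sentence is read. It states "Differences in adverse events between arms will be tested using chi-square tests", and for all analyses "two-sided tests will be used and p-values less than 0.05 will be considered as statistically significant".

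No section gives an expected adverse-event rate, or the probability that either rule fires when the two agents are equally safe.

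**The concern.** In the Protection sentence the adverb sits next to the pain scores. The adverse-event part, taken as written, is a bare comparison between arms with a mandatory stop attached. Study Design has every patient contacted at two weeks about adverse effects of any kind, so ungraded and unattributed events would feed that comparison.

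With about 10 patients per arm, two equally safe agents will often differ by an event or more, and by symmetry BS has the higher count in half of those cases. A stop at 20 of the 76 planned patients would leave both aims unanswered and could be taken for a safety signal against BS.

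The same data can also lead to different actions. One more mild, unrelated event on BS calls for stopping under one section and for nothing under the other. Someone conducting the look could not tell from the protocol which applies.

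**Working it through.** **The plan's own figures.** The only design figure that can be reproduced is the sample size: "At test significance level (α) = 0.05 with 80% power", a difference of 14 and an SD of 20. The noncentral t gives 79.97% power at 33 per group and 81.2% at 34, so 34 per group is right. Then 68 / 0.90 = 75.6, which rounds up to 76. No operating characteristic is stated for either stopping rule, so there is none to reproduce.

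**Inputs.**
- Look at 20 patients (Protection).
- Split of 10:10. This is an assumption: Study Design describes randomization in an Excel table and mentions no blocking.
- Per-patient event rate p, equal in both arms. The documents do not give it, so 1% to 30% is shown.
- Each patient counts once, as having an event or not (assumption).

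**Literal trigger.** Let X (BS) and Y (lidocaine) be independent Binomial(10, p). By symmetry P(X > Y) = [1 − P(X = Y)] / 2, where P(X = Y) is the sum over k of P(X = k)².

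At p = 5%, P(X = 0, 1, 2, 3) = 0.5987, 0.3151, 0.0746, 0.0105. The squares sum to 0.3585 + 0.0993 + 0.0056 + 0.0001 = 0.4635. Hence P(X > Y) = (1 − 0.4635) / 2 = 0.268.

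**Comparators, same enumeration.**
- *Tested reading:* the word significantly governs both parts. The trigger is z = (X/10 − Y/10) / √[q(1 − q)(2/10)] > 1.96, with q = (X + Y)/20. This is the uncorrected two-sided 0.05 chi-square, counted in the BS direction.
- *Stopping Rule section:* X + Y ≥ 5 and X > Y, evaluated once at 20 patients. Here p is the rate of qualifying events (grade 2 or higher, at least possibly related).

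| Assumed p, both arms | Tie | Literal trigger | Tested reading | Stopping Rule section |
|---|---|---|---|---|
| 1% | 82.6% | 8.7% | 0.0% | 0.0% |
| 3% | 59.7% | 20.2% | 0.01% | 0.01% |
| 5% | 46.3% | 26.8% | 0.06% | 0.1% |
| 10% | 31.3% | 34.4% | 0.45% | 2.0% |
| 20% | 22.4% | 38.8% | 1.5% | 16.1% |
| 25% | 20.5% | 39.7% | 1.7% | 24.9% |
| 30% | 19.3% | 40.3% | 1.9% | 32.0% |

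The last column should not be read straight across. Qualifying events are a subset of all adverse events, so their rate is no higher.

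**Sensitivity to the split.** Under simple unblocked randomization, at p = 5%, 10%, 20% and 30%:
- literal trigger comparing counts: 27.1%, 35.0%, 39.9%, 41.8%;
- literal trigger comparing rates: 31.1%, 42.0%, 46.5%, 47.0%;
- tested reading: 0.4%, 1.1%, 2.1%, 2.5%.

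**Unequal rates, literal trigger, 10:10.** P(X > Y) for BS vs lidocaine is 16% at 10% vs 20%, 62% at 20% vs 10%, 81% at 30% vs 10% and 92% at 40% vs 10%.

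**Choice of test.** For 4 vs 0 events, q = 0.2 and z = 0.4 / √(0.2 × 0.8 × 0.2) = 2.24, so the uncorrected chi-square gives p = 0.025. Fisher's exact test on the same table gives p = 0.087, and 5 vs 0 gives 0.033. The tested reading therefore still needs its test named.

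**The case against.** The strongest reply is that the sentence need not be read literally. The sentence before it asks for concerning trends in pain scores and adverse events together, the adverb can govern both parts, and Data Analysis already plans a chi-square test at 0.05. On that reading the false-stop chance is about 2% or less for rates up to 30%. This stands as a possible reading, but it does not settle the matter. The Stopping Rule section also uses significantly for pain and only a higher rate for adverse events, which supports the literal reading. A mandatory stop whose false-stop chance could be 2% or 40%, depending on the reach of one adverb, needs rewording either way.

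Second, the percentages rest on an assumed event rate. This stands in full. The only nearby text is a manufacturer statement, quoted under Potential Risks, that reactions to 0.9% benzyl alcohol are not known to occur; it fixes no all-cause two-week rate. A reader might infer that the plan has a false-stop rate of 27–40%. The documents do not support that: it needs a rate of about 5–30%, and below that the figure is lower, with ties the commoner outcome at 3%.

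Third, a reader might infer that a stop under the literal trigger would carry almost no information. That is wrong. The trigger fires 16% of the time when BS has half the lidocaine rate and 81% when BS has three times it (30% vs 10%). Its specificity is low, but it does discriminate.

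Fourth, how cautious an early safety look should be is for the sponsor to judge. This also stands, and it is why the point does not ask that either trigger be preferred. Nor do the documents say that the Protection sentence overrides the Stopping Rule section; they leave the two unreconciled.

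**Conclusion.** The point holds as a conflict between two stated rules, one of which, read literally, would often stop the study on chance. They differ on which events count, how many are needed and what follows. With 10 per arm and equal true rates, the literal Protection trigger stops the study by chance in about 9% of trials at a 1% event rate, rising to 40% at 30%. The alternatives behave very differently: about 2% or less (rates up to 30%) for the tested reading, and 0.1%, 2%, 16% and 25% for the Stopping Rule section at qualifying-event rates of 5%, 10%, 20% and 25%.

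All these figures depend on assumed rates. The tested figure also depends on the 10:10 split: unblocked allocation takes it to 2.5% at a 30% rate. The conflict in wording depends on neither assumption. It should be corrected, because a stop at this look decides whether the trial answers its question at all.

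**What to change.** Reconcile the Protection sentence with the Adverse Event Stopping Rule section so that one rule governs the 20-patient look. The rule should state:

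1. one trigger: which events count (grade, attribution, patients or events), and the threshold or named test, chosen by the sponsor's safety team;
2. one consequence: review, suspension or stop. The pain trigger needs the same alignment, since the two sections also differ on its consequence;
3. its false-stop probability under equal rates, over a range of assumed event rates.

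If a significance test is intended for adverse events, the sentence should say so and name the test, given how far the chi-square and Fisher results differ at this size.

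The cost is a short protocol amendment and a calculation of the kind shown above. The downside is that, if the bare numerical trigger is not kept, a small true excess on BS would no longer stop the study automatically at 20 patients. The study team's discretion to suspend accrual for unexpected adverse-event profiles, already in the Stopping Rule section, would remain.
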